**Revision History**

Version #	Date (DD-Mmm-YYYY)	Document Owner	Revision Summary
2.0	12-MAY-2021	████████	

Planned analyses revised to remove submission of 6M analysis data and unblinding after second DMC review

Alpha adjustment updated; response rate during Month 9 moved from secondary endpoint to exploratory

Clarifications made to rules for handling missing and impacted data due to COVID-19 for responder analyses

Clarifications added to multiple imputation process

Reorganization of primary endpoint analysis sections in 9.2 to match a protocol amendment; supplemental analysis section added and sensitivity analyses for mITT and PP populations moved to supplemental analysis

Supplemental analysis of response endpoints using logistic regression in imputation model added.

Summary of infusion reactions/anaphylactic reactions by ADA status added; summary of gout flares by 3 month intervals added; summary of AEs occurring on commercial pegloticase or MTX added

Changes from protocol were removed since a protocol amendment incorporated the changes listed in version 1.0 of the SAP.

3.0	23-SEP-2021	████████	

Tipping point analysis added as sensitivity to primary endpoint analysis.

Supplemental analysis for primary endpoint added looking at response when a single sUA > 6 mg/dL stopping rule is applied.

Modifications made to the handling of data in subjects impacted by COVID-19; imputation for primary endpoint will be used only for subjects who have missing data during time of primary endpoint due to site closure from COVID-19.

Clarifications added for the analysis of tophi data.

Compliance calculation for MTX updated.

Other minor clarifications and grammatical corrections made.

This document is confidential.

I confirm that I have reviewed this document and agree with the content.

Approvals		
Syneos Health Approval		
		
Name, Title Lead Biostatistician	Signature	Date (DD-Mmm- YYYY)
		
Name, Title	Signature	Date (DD-Mmm- YYYY)
Horizon Therapeutics Approval		
		
Name, Title Sponsor Contact	Signature	Date (DD-Mmm- YYYY)
		
Name, Title Sponsor Contact	Signature	Date (DD-Mmm- YYYY)
		
Name, Title Sponsor Contact	Signature	Date (DD-Mmm- YYYY)

This document is confidential.

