- Serious TEAEs
- TEAEs related to MTX or placebo
- TEAEs related to pegloticase (applicable to Pegloticase + IMM Period only)
- Serious TEAEs related to MTX or placebo
- Serious TEAEs related to pegloticase (applicable to Pegloticase + IMM Period only)
- TEAEs with an Rheumatology CTC Criteria of 3 or higher
- TEAEs leading to permanent withdrawal of MTX or placebo
- TEAEs leading to permanent withdrawal of pegloticase (applicable to Pegloticase + IMM Period only)
- TEAEs related to MTX or placebo leading to permanent withdrawal of MTX or placebo
- TEAEs related to pegloticase leading to permanent withdrawal of pegloticase (applicable to Pegloticase + IMM Period only)
- TEAEs leading to death

For Pegloticase + IMM Period, the number and percentage of subjects as well as the number of events with any infusion reactions including/excluding anaphylaxis will be included in the summary. In addition, the overall summary of TEAEs during the Pegloticase + IMM Period based on subgroup will be provided.

Using the safety population, an overall summary of AEs occurring during the follow-up period (with onset more than 30 days after the last dose of study medication), including the number and percentage of subjects with each AE type as well as the number of events for each of the following:

- AEs
- Serious AEs
- AEs with an Rheumatology CTC Criteria of 3 or higher
- AEs leading to death

Percentages for the overall summary of AEs during follow-up will be based on the number of subjects who had follow-up more than 30 days after last dose of medication.

Additional AE summaries will be provided by onset period, including the number, percentage of subjects, experiencing TEAEs for the following:

This document is confidential.

- TEAEs overall and by SOC and PT for the: MTX Tolerability Assessment Period, Run-in Period, Pegloticase + IMM Period, and Follow-up Period
- TEAEs by maximum severity, overall and by SOC and PT for the MTX Tolerability Assessment Period, Run-in Period, and Pegloticase + IMM Period
- TEAEs related to MTX or placebo overall and by SOC and PT for the MTX Tolerability Assessment Period, Run-in Period, and Pegloticase + IMM Period
- TEAEs related to pegloticase overall and by SOC and PT for the Pegloticase + IMM Period only
- TEAEs Related to MTX or placebo by maximum severity, overall and by SOC and PT for the: MTX Tolerability Assessment Period, Run-in Period, and Pegloticase + IMM Period.

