- TEAEs Related to Pegloticase by maximum severity, overall and by SOC and PT for the Pegloticase + IMM Period only
- Serious TEAEs, overall and by SOC and PT for the: MTX Tolerability Assessment Period, Run-in Period, Pegloticase + IMM Period, and Follow-up Period
- TEAEs leading to permanent withdrawal of MTX or placebo, overall and by SOC and PT for the: MTX Tolerability Assessment Period, Run-in Period, and Pegloticase + IMM Period)
- TEAEs leading to permanent withdrawal of pegloticase, overall and by SOC and PT for the Pegloticase + IMM Period only
- COVID-19 Infection TEAEs by maximum severity, overall and by SOC and PT for the: MTX Tolerability Assessment Period, Run-in Period, Pegloticase + IMM Period, and Follow-up Period

In addition, the summary of TEAEs by SOC and PT during the Pegloticase + IMM Period based on subgroup will be provided. Also, AEs that occur after the start of commercial pegloticase will be summarized by SOC and PT and relationship to commercial pegloticase for subjects who take commercial pegloticase after discontinuation of study pegloticase. Similarly, AEs that occur after the start of commercial MTX will be summarized by SOC and PT and relationship to commercial MTX for subjects who take commercial pegloticase after discontinuation of study MTX. The tables summarizing commercial product use will only be created if at least 25 subjects take commercial product.

The incidence per person years of exposure to MTX or placebo and incidence per person years of exposure to pegloticase will be provided on all tables except those summarizing events by maximum intensity, and those for the post-treatment follow-up period. The person years (PY) of exposure is defined as  $[(\text{last treatment date in the period} - \text{first treatment date in the period} + 1)/365.25]$ . Total PY of exposure to pegloticase will be calculated separately for each treatment arm.

For summaries by SOC, PT, and maximum severity, a subject will only be counted once for each SOC based on the maximum intensity level reported for that SOC and once for each unique PT

This document is confidential.

within that SOC level at the maximum intensity level reported for that PT. For summaries by SOC and PT only, a subject will be counted at most once at the SOC level and at most once at each unique PT within the SOC level. Summaries presenting the frequency of TEAEs by SOC and PT will be ordered alphabetically by SOC and then, within a SOC, alphabetically by PT.

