In addition to the listing of all AEs, separate listings will be provided for serious AEs, AEs leading to withdrawal of MTX or placebo, AEs leading to withdrawal of pegloticase, AEs leading to study discontinuation, AEs of special interest, COVID-19 AEs, AEs occurring while taking commercial pegloticase and/or MTX, adjudicated AEs, and AEs leading to death. TEAEs and the period of onset will be identified on each listing.

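### SAP 11.3 defines the commercial-MTX adverse event table by events after commercial MTX but takes its subjects from users of commercial pegloticase, so anyone on commercial MTX alone would be left out of it

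*SAP*

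**What the plan says.** SAP 11.3 (Adverse Events) describes two tables of adverse events after subjects move from study drug to commercial product.

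- **Commercial pegloticase.** Events after its start are tabulated by SOC and PT and by relationship to commercial pegloticase, "for subjects who take commercial pegloticase after discontinuation of study pegloticase".
- **Commercial MTX.** "Similarly, AEs that occur after the start of commercial MTX will be summarized by SOC and PT and relationship to commercial MTX", and the sentence then ends "for subjects who take commercial pegloticase after discontinuation of study MTX".

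Both tables share one condition: "The tables summarizing commercial product use will only be created if at least 25 subjects take commercial product".

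Three other places bear on how this should be read. The list of planned listings later in SAP 11.3 includes one for "AEs occurring while taking commercial pegloticase and/or MTX". The same section plans, for the safety population, "an overall summary of AEs occurring during the follow-up period". The SAP Revision History entry for version 2.0 records the addition as "summary of AEs occurring on commercial pegloticase or MTX added". I use that entry only as a sign of intent.

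**The concern.** The events, the relationship assessment and the subjects of a table should all refer to the same product. In the MTX sentence the first two refer to commercial MTX and the third to commercial pegloticase. This is an operative specification that a programmer would code from, not background text.

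At stake is who is represented in the one described summary that classifies events by relationship to commercial MTX. If the mismatch is noticed only after unblinding, someone has to decide then who belongs in a safety table. That choice is easy to avoid now.

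**Working it through.** No arithmetic applies. The SAP gives no figure to reproduce, and the point depends on no alpha, power, effect size or sample size. The check is a comparison of the two sentences, followed by a walk through the possible subjects.

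**Step 1: element by element (SAP 11.3).**

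| Element | Pegloticase table | MTX table |
|---|---|---|
| Events counted after the start of | commercial pegloticase | commercial MTX |
| Relationship assessed to | commercial pegloticase | commercial MTX |
| Subjects who take | commercial pegloticase | commercial pegloticase |
| After stopping | study pegloticase | study MTX |

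The left column agrees with itself. In the right column the third row does not match the other three.

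**Step 2: each kind of subject under the literal MTX rule** (all having stopped study drug).

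| Commercial MTX | Commercial pegloticase | In literal subject set? | Can have an event after commercial MTX starts? | Result |
|---|---|---|---|---|
| Yes | Yes | Yes | Yes | Handled correctly |
| Yes | No | No | Yes | Omitted from this table |
| No | Yes | Yes | No | In the set, contributes no event |
| No | No | No | No | Not relevant |

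The second row is the omission. The third row adds subjects who cannot have a qualifying event. The sentence states no denominator. SAP 13.2.5.2 defaults to subjects in the analysis set who have an observation, so whether third-row subjects would enter a percentage depends on the programmer's reading.

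**Step 3: where the omitted events still appear.** They are in the listing of all adverse events and in the commercial-product listing, which covers use of either product or both. If onset is within 30 days of the last study dose, they fall in the Pegloticase + IMM tables. If later, they fall in the follow-up tables and the overall follow-up summary. None of these classifies events by relationship to commercial MTX in a table.

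**Step 4: signs of intent.** The MTX sentence presents itself as the counterpart of the one before it. The listing joins the two products with and/or, and the revision entry joins them with or. All three point to commercial MTX as the intended product. No sentence in either document says that the table is for users of both.

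**The case against.** The strongest reply is that this is an evident slip of one product name, that the surrounding text shows what was meant, and that a careful programmer would code it correctly. The evidence of intent does stand. The literal rule remains on the page, however, and a specification should not rely on being read against its own words.

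A second reply is that the restriction may be deliberate. Protocol 7.2 presents MTX as co-therapy to reduce pegloticase immunogenicity, so a table for users of both products would be coherent. That is possible, but it is not stated.

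A third reply is that commercial MTX alone may hardly occur. Protocol 9.3.3.1.1 and 9.4.1.1 stop study MTX or placebo when pegloticase stops. Exclusion criterion 4 bars current or chronic MTX users at entry, and Protocol 9.4.10 restricts non-study MTX through the end of treatment. The documents give no particular reason for MTX alone in these subjects, so this reply stands as a limit on size.

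Some stronger readings are tempting but unsupported:

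- **That these subjects' events are lost to the report.** They are missing from one table only, as Step 3 shows.
- **That events would be counted in the wrong group.** Only events after the start of commercial MTX qualify, so a subject on commercial pegloticase alone adds none.
- **That some share of commercial-MTX users would be dropped.** The documents give no frequency from which to estimate one.
- **That placebo-arm subjects are outside the clause.** All randomized subjects were to take open-label study MTX from Week -6 to Week -4 (SAP 3.8), so they too have stopped study MTX. Naming placebo is a clarification.
- **That the 25-subject condition is an error because it is not set per product.** The SAP leaves this unstated, which is a missing detail. Separate thresholds could only make each table less likely to be produced.

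**Conclusion.** The subject clause of the commercial-MTX table is wrong as written, unless a restriction to users of both commercial products was intended and left unsaid. Read literally, it omits subjects on commercial MTX alone from this dedicated table and admits subjects on commercial pegloticase alone, who can contribute nothing to it.

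The consequence is minor. The number of subjects affected is unknown and may be zero. The table is descriptive and conditional on at least 25 users of commercial product, and it has no bearing on the primary or secondary endpoints. It concerns commercial product taken after study drug.

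Two assumptions remain. I take the table to be the only one describing events by relationship to commercial MTX. The text of SAP 11.3 supports this, but the Index of Tables is redacted, so titles could not be checked. I also take the carry-over to be unintended, on the evidence in Step 4.

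**What to change.** In the commercial-MTX sentence of SAP 11.3, replace *commercial pegloticase* in the subject clause with *commercial MTX*, and extend the closing words to *study MTX or placebo for MTX*. If a table limited to users of both commercial products was intended, say so explicitly instead.

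The cost is one SAP sentence and the matching line of the programming specification. No data collection, sample size or inferential analysis changes. It should be settled before unblinding.

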All subjects who complete the Run-in Period will receive the first pegloticase infusion on Day 1. All subsequent doses and study visits will be scheduled based on the Day 1 visit date.

It is required that before a subject begins the pegloticase + IMM Period, he or she has been taking at least one protocol standard gout flare prophylaxis regimen (i.e. colchicine and/or non-steroidal anti-inflammatory drugs and/or low-dose prednisone  $\leq 10$  mg/day) for  $\geq 1$  week before the first dose of pegloticase and continues flare prophylaxis per American College of Rheumatology guidelines [Khanna D et al. 2012] for the greater of 1) 6 months, 2) 3 months after achieving target serum urate (sUA  $< 6$  mg/dL) for patients with no tophi detected on physical exam, or 3) 6 months after achieving target serum urate (sUA  $< 5$  mg/dL) for patients with one or more tophi detected on initial physical exam that have since resolved. For IR prophylaxis, fexofenadine (180 mg orally) will be taken the day before each infusion; fexofenadine (180 mg orally) and acetaminophen (1000 mg orally) will be taken the morning of each infusion; and methylprednisolone (125 mg IV) given over an infusion duration between 10 - 30 minutes, initiated immediately prior to each infusion.

During the Pegloticase + IMM Period, pegloticase 8 mg will be administered intravenously (IV) every 2 weeks from Day 1 through the Week 50 Visit for a total of 26 infusions; pegloticase will be administered after all pre-dose study visit assessments have been completed at each visit. The date and start and stop time of infusion will be recorded. Serum uric acid stopping rules will be applied: subjects with sUA level  $> 6$  mg/dL at 2 consecutive study visits beginning with the Week 2 Visit will discontinue treatment, complete the End of Pegloticase Infusion Visit procedures within 2 weeks and continue the subject visits according to the protocol (without treatment).

During the Pegloticase + IMM Period, subjects will be instructed to take MTX or placebo for MTX weekly on the same day each week, within 1 to 3 days prior to each pegloticase infusion and one additional weekly dose after the last infusion for subjects who have not stopped pegloticase due to sUA stopping rules; however, if a subject does not do so, MTX or placebo for MTX must be taken  $\geq 60$  minutes prior to each pegloticase infusion.

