### **11.3. Adverse Events**

All adverse events will be coded using MedDRA version 23.1. AE monitoring will begin from the signature of the Informed Consent Form (ICF) until the 6 month Post Treatment Follow-up Visit. SAE monitoring will begin from the signature of the ICF until the 6 month Post Treatment Follow-up Visit.

Adverse events with an onset date strictly prior to the first MTX treatment in the MTX Tolerability Assessment Period will be called non-treatment-emergent events.

Treatment-emergent AEs (TEAEs) for the MTX Tolerability Assessment Period are defined as events with an onset date on or after the first dose of MTX (but not on or after the first MTX or placebo date in subjects who entered the Run-in Period) through 30 days after the last dose of MTX for subjects who did not receive MTX or placebo in Run-in Period.

Treatment-emergent AEs (TEAEs) for the Run-in period are defined as events with an onset date and time on or after the first dose of MTX or placebo in the Run-in Period (but not on or after the first infusion date of pegloticase in subjects who entered the Pegloticase + IMM Period) through 30 days after the last dose of MTX or placebo for subjects who did not receive pegloticase.

TEAEs for the Pegloticase + IMM Period are defined as events that occur on or after the start date and time of the first pegloticase infusion through 30 days after the last dose of pegloticase and/or MTX or placebo (whichever is later).

Adverse events with an onset date more than 30 days after the last dose of pegloticase and/or MTX or placebo (whichever is later), will be adverse events in the follow-up period.

All AEs, both serious and non-serious, will be assessed for severity using the Rheumatology Common Toxicity Criteria (CTC) v2.0. Missing data conventions for AEs are described in Section 6.3.2. The imputed onset dates will be used to determine the period of onset. Summaries of TEAEs in the MTX Tolerability Assessment Period will be provided using the MTX Population. Summaries of TEAEs in the Run-in Period and in the Pegloticase + IMM Period will be provided for the safety population.

An overall summary of TEAEs will be provided for the MTX Tolerability Assessment Period. TEAEs will be presented by treatment group for the Run-in Period and Pegloticase + IMM Period. Summaries will include the number and percentage of subjects with each AE type as well as the number of events for each of the following:

This document is confidential.

- TEAEs

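### SAP 11.3 counts adverse events for 30 days beyond the last dose but stops person-years on the last dose, so the planned rates per person-year mix two windows and do not name their numerator

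*SAP*

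**What the plan says.** All of the following is in SAP 11.3 unless another section is named.

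- **Denominator.** "The person years (PY) of exposure is defined as" the last treatment date in the period minus the first, plus one day, divided by 365.25. No time after the last dose is credited.
- **Numerator window, Pegloticase + IMM Period.** Events count from the first infusion "through 30 days after the last dose of pegloticase and/or MTX or placebo (whichever is later" of the two). The MTX Tolerability Period has a similar tail, "through 30 days after the last dose of MTX for subjects who did not receive MTX or placebo in Run-in Period".
- **Where the rates appear.** There is one rate per person-year of MTX or placebo and one for pegloticase: "incidence per person years of exposure to pegloticase will be provided on all tables", except the maximum-intensity and follow-up tables.
- **Counting unit.** The overall summaries give numbers of subjects "as well as the number of events for each of the following" category. The further tables are described as "including the number, percentage of subjects, experiencing TEAEs for the following" list, and for SOC/PT tables "a subject will be counted at most once at the SOC level" and at most once per preferred term. The sentence that introduces the rates does not say which count is divided by person-years.
- **Dosing after the last infusion.** SAP 3.5 schedules MTX or placebo "within 1 to 3 days prior to each pegloticase infusion and one additional weekly dose after the last infusion" for subjects who have not met the sUA stopping rule. The Week 50 note in Protocol 9.5.8.2.28 puts that dose one week after the Week 50 visit.

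**The concern.** A rate per person-year is interpretable only if the events and the time come from the same window. Here every subject followed for the full tail contributes at least 30 days in which events can count but no time accrues. The shortfall is roughly fixed in days, so it weighs more the shorter the treatment. The reported rate then reflects how long subjects stayed on treatment as well as how often events occurred.

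The unnamed numerator adds a second uncertainty. Two programmers could follow the text exactly and produce different rates for the same table. Because these rates are planned for most adverse-event tables, the definition should be settled before the tables are produced.

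**Working it through.** **Input from the plan.** SAP Table 1 (Section 6.4) gives Day 351 as the target for Week 50. This reproduces: 50 × 7 + 1 = 351. The plan states no person-year total and no adverse-event rate, so there is no further figure to reproduce.

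**Completer, pegloticase denominator.** Exposure is 351 − 1 + 1 = 351 days (351/365.25 = 0.961 person-years). The event window ends 30 days after the later last dose. A weekly dose taken 1 to 3 days before each infusion next falls 4 to 6 days after the Week 50 infusion, on Day 355 to 357. The Protocol's Week 50 note gives Day 358.

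| Last MTX/placebo dose | Event window (days) | Window / exposure |
|---|---|---|
| None after Week 50 | 351 + 30 = 381 | 381/351 = 1.085 |
| Day 355 | 385 | 385/351 = 1.097 |
| Day 357 | 387 | 387/351 = 1.103 |
| Day 358 | 388 | 388/351 = 1.105 |

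These are ratios of denominators. The same events are divided by 351 days in one rate and by 381 to 388 days in the other, so the ratio does not depend on when the events occur.

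**If events were cut at the last dose instead.** With a share s of events in the tail, the rate as written exceeds the cut rate by 1/(1 − s) − 1. That is 0% for s = 0 and 5.3% for s = 0.05. The documents give no value for s.

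**Early stoppers.** Protocol 9.3.3.1.1 stops MTX/placebo when infusions cease, so the gap is at least 30 days if the subject is followed throughout:

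- last infusion Day 169: (169 + 30)/169 = 1.178
- last infusion Day 99: (99 + 30)/99 = 1.303

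Under the sUA stopping rule the gap can be longer. The infusion is withheld at the visit about 14 days after the last one, and weekly doses can be taken before then, about 4 to 6 and 11 to 13 days after the last infusion. If both are taken, the gap is 11 + 30 = 41 to 13 + 30 = 43 days:

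- Day 169: 41/169 = 24% to 43/169 = 25%
- Day 99: 41/99 = 41% to 43/99 = 43%

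**If subjects are the numerator.** Against subjects per total window-matched person-years, the ratios above carry over, because the numerator is again the same. Against a first-event rate they do not, because person-years are not cut at the first event and this pulls the rate down. As an illustration, assume a constant hazard and cumulative incidence p over a 381-day window. Then reported/true = p × 381 / (351 × (−ln(1 − p))), which is 1.058 at p = 0.05 and 0.783 at p = 0.50.

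**Tolerability period.** Two weekly doses, on Days 1 and 8, give 8 days of exposure. A subject never given blinded drug has an event window of 8 + 30 = 38 days (38/8 = 4.75), provided events are collected that long. This period has a single column and no arm comparison.

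**The case against.** The strongest reply is that the SAP calls the denominator exposure, not time at risk, and exposure properly ends at the last dose. That is a legitimate convention, but off-treatment events then do not belong in the numerator, and no passage removes them. The monthly gout-flare percentages in SAP 11.3.1 do not settle the intent. Their text includes the 30 days after treatment, while their Month 2 example requires a dose on Day 31 or later.

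A second reply is that 8.5% to 10.5% assumes a constant event rate through a tail with no infusions. This holds only if the comparison is with events cut at the last dose. It does not affect the comparison with window-matched person-years.

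A third reply is that the SOC/PT tables already fix the unit as subjects. They fix it for the counts, but the text does not extend it to the rate, and the overall summaries carry both units. This part of the reply narrows the ambiguity without removing it.

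A reader might also infer that the mismatch favours the MTX arm, because more placebo subjects are expected to lose response and stop early. The documents do not support that step. The 71% and 43% planning figures are response rates, and neither document gives time on treatment by arm.

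**Conclusion.** The point stands as a definitional flaw worth correcting, of modest consequence. Followed exactly, SAP 11.3 gives rates whose numerator and denominator cover different windows. For an event-count rate per pegloticase person-year, measured against window-matched person-years, the excess is:

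- **Completer:** 8.5% with no dose after Week 50, rising to 10.5% with the extra dose on Day 358.
- **Last infusion Day 169:** at least 17.8%, and about 24% to 25% if both weekly doses precede a stopping-rule discontinuation.
- **Last infusion Day 99:** at least 30%, and about 41% to 43% in the same case.

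These figures assume on-schedule visits and follow-up through the whole tail. The rate's numerator also remains unspecified.

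It would be wrong to read this as undermining the safety conclusions. The rates are descriptive, and the Fisher tests in Protocol 9.6.7 compare proportions. Infusion reactions are defined mainly by onset during or within 2 hours after an infusion (SAP 11.3.1), so few can fall in the tail. No between-arm effect is claimed.

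**What to change.** In SAP 11.3, for the treatment-emergent event rates:

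1. Replace person-years of exposure with person-years at risk over the same window as the event definition for that period. This runs from the first dose in the period to the earliest of 30 days after the later last dose, the start of the next period, death or last contact.
2. If separate pegloticase and MTX/placebo exposure rates are kept, count in each only events up to that drug's own last dose. Cutting both at the later drug would still set events to Day 358 against 351 pegloticase days (358/351 = 1.020).
3. State for each table whether the numerator is events or subjects. If subjects, either cut person-years at the first event or label the rate as subjects with an event per total person-years.

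No new data are needed. The cost is a little more derivation code. Cutting at the first event costs most, because each term in each arm then needs its own denominator. Event-count rates will fall, or stay the same if events are cut at the last dose and none occur in the tail.
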